A power analysis (G*Power) was conducted to determine the number of participants needed to achieve this goal. For repeated measures analyses, 44 participants are required in order to reach a medium effect size of .25 with an adequate power of .80 at $\alpha = .05$ (Faul et al., 2009) to determine interaction effects of between and within participants' factors. Convenience sampling via advertisement through social media, mail groups, and on campuses was used to collect participants. Initially, 178 adult participants were recruited for this study to reach adequate power for multivariate analysis. Participants randomly and equally were assigned to the experimental group (89 participants) and control group (89 participants) to see whether the combined training program was effective for the general population. 33 participants for the experimental group and 48 participants for the control group completed the posttest. However, after checking outliers and normality analysis, 31 participants for the experimental group (28 female, 3 male), and 34 participants for the control group (29 female, 5 male) were included in the further analyses. Please see the figure 6.1. the flow of participants through each stage of the study. The details of the participants were presented the Table 6.1. Demographic Characteristics. To reduce drop-out, incentives such as drawing for money/prizes were used. Inclusion criteria for adult participants are being aged 18 or above, being able to use computers, smartphones, or tablets, being native Turkish citizens, having no record of any psychiatric disorders, and having no record of any physical and neurological conditions that prevent to use of technological devices. Participants who are under the age of 18 and have any record of psychiatric and physical conditions that prevent to use of technological devices were excluded from the study.

Materials

Self-Report Questionnaires

Figure 1. The Flow of Participants

Demographic Information Form

Basic information such as age, gender, education level (i.e., undergraduate, postgraduate), and income was obtained from the participants, and it was developed by the researcher.

Autism Quotient (AQ) for Adults Turkish Version (Baron-Cohen et al., 2006; Baron-Cohen et al., 2001a; Köse et al., 2010)

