To measure autistic traits, the Autism Quotient (AQ; Baron-Cohen et al., 2001) was used. AQ for adults is adapted to Turkish culture by Köse and colleagues (2010). The self-report questionnaire consists of 50 questions using a Likert-scale rating; “definitely agree”, “slightly agree”, “slightly disagree”, and “definitely disagree”. In the Turkish adaptation of the AQ for adults, Cronbach’s alpha value for this scale is .64, and test-retest reliability is $r = .72$. The AQ is a widely used assessment tool that measures five subscales: social skills, communication, attention to detail, attention switching, and imagination. It is available in different languages (e.g., Turkish by Köse et al., 2010; Dutch by Hoekstra et al., 2008; Japanese by Wakabayashi et al., 2006).

Depression Anxiety Stress Scale 21(DASS – 21; Lovibond & Lovibond, 1995; Sarıçam, 2018)

DASS-21 is a self-report scale to examine depression, anxiety, and stress levels for adults by Lovibond and Lovibond (1995). The Turkish adaptation study for DASS-21 was conducted by Sarıçam (2018). This scale consists of three subscales, one for depression, one for anxiety, and one for stress. The total number of items is 21. For this scale, inter-scale reliability with Cronbach’s Alpha is .87 for depression, .85 for anxiety, and .81 for stress subscales. Test-retest reliability is $r = .68$ for depression, .66 for anxiety, and .61 for stress.

Performance Tasks

It was administered the following performance tasks to evaluate executive functions such as cognitive flexibility, WM, and inhibitory control, as well as social cognition including cognitive empathy and affective empathy. To ensure standardized measurement, we recorded the errors for each task based on previous intervention studies (Chooi & Logie, 2020; de Vries et al., 2015;

Macoun et al., 2021; Maraver et al., 2016). Each task begins with a non-scored trial to ensure that participants understand the task before scoring begins. The only exceptions are for the self-assessment manikin for affective empathy, and the Eyes Test for which detailed information was provided.

Wisconsin Card Sorting Task (WCST; Berg, 1948)

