and-white photographs of human eyes. For each photograph, participants were asked to choose which of 4 words best describes what the person in the photograph is feeling or thinking. The version used was adapted for Turkish by Girli (2014). The Cronbach alpha internal consistency coefficient for this test is greater than .70. Accuracy of the test was measured.

Self-Assessment Manikin (SAM; Bradley & Lang, 1994)

Self-Assessment Manikin was carried out to measure self-reported emotional responses to facial expression images for affective empathy. Karolinska Directed Emotional Faces (KDEF, Conley et al., 2018; Lundqvist et al., 1998) were used to express facial emotions. In total, 30 images (15 male, 15 female) were chosen and seven emotional expressions including happiness, neutral, anger, fear, and disgust were depicted. The task requires participants to examine each facial expression and rate how they feel it on a valence scale (more negative (1) to more positive (9)). The tasks were adapted from Wai and Tiliopoulos (2012). Valence scores for each emotion were obtained by summing responses for all images.

Procedure

Approval from the ethical committee of Ibn Haldun University was obtained for this study (No. E-71395021-050.06.04-34359) and the protocol ID of clinical trials was obtained (NCT06213194). The participants for the study were recruited using convenience sampling through advertisements on social media, mail groups, and campuses. Once recruited, all participants completed pretest questionnaires and tasks before assigning them to the groups and undergoing training on the *MindZone* training website (www.mindzone.com.tr). 31 participants

for the experimental group (28 female, 3 male), and 34 participants for the control group (29 female, 5 male) were included for the study. The experimental group underwent an online 6-week training period through the website developed by the researcher (www.mindzone.com.tr), while the control group was placed on a waiting list. Posttests were collected at the end of the 6th week from both experimental and control groups. Additionally, the researcher and research assistant checked each participant's progress weekly, sent reminder messages, and made phone calls to improve training continuity if participants had not completed the requirements. Details about training are presented in Table 5.2. *MindZone* Manual (see Chapter 5). After the

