completion of the research studies, the control group (on the waiting list) is scheduled to access the online training program in accordance with ethical guidelines.

Data Analysis

The data from the current study was analyzed using the SPSS 25.0 package. Initial analyses were performed to determine if the data showed a normal distribution. Before conducting parametric tests, the Shapiro-Wilk test, box plots, and skewness and kurtosis scores were used to check for normal distribution. The self-report questionnaires' data was found to be normally distributed according to the Shapiro-Wilk test ($p > .05$). As for the performance tasks, the skewness and kurtosis of the data fell within an acceptable range for applying parametric tests, as specified by Hair and colleagues (2010). Covariate analyses were conducted to account for the effects of autistic traits in the intervention model. Before including covariates in the analyses, correlation analyses and tests for homogeneity of regression slopes were performed according to the assumptions of covariance (Field, 2013). The results showed that only communication and attention-switching had significant correlations with dependent variables ($p < .05$) and met the assumptions for being used as covariates for mental health symptoms (Field, 2013). Regarding EFs and social cognitive skills, communication, attention to detail and imagination entered as covariates in the model ($p < .05$); however, only communication met the assumptions for homogeneity of regression slopes for EFs and social cognitive skills (Field, 2013). All correlation tables for these assumptions were presented in Appendix C, D, and E. Moreover, t-test analysis was carried out to see whether the pretests of dependent variables and AQ and its subscales for experimental and control groups

differ. Due to more than 8 variables; a conservative p -value was set ($p = .01$). The results showed no significant differences in all pretest scores and AQ (all $ps > .01$).

In the experimental study, 2 x 2 mixed design repeated measure ANOVAs were conducted to examine the group (experimental and control group) and the effects of time (pretest and posttest) on mental health (DASS-21 and its subscales), as well as executive functions (working memory, inhibitory control, and cognitive flexibility), and social cognitive skills (cognitive empathy and affective empathy). In terms of performance tasks, to ensure standardized measurement, errors

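### Sixteen of 81 posttest completers (14 of 48 control, 2 of 33 experimental) were dropped after outlier and normality checks with no stated removal rule, and no analysis of all 81 is described

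*Combined protocol and SAP*

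**What the plan says.** The Participants section describes the allocation: "Participants randomly and equally were assigned to the experimental group (89 participants) and control group (89 participants"). It then gives the posttest numbers: "33 participants for the experimental group and 48 participants for the control group completed the posttest". The next sentence reduces these: "However, after checking outliers and normality analysis, 31 participants for the experimental group (28 female, 3 male), and 34 participants for the control group" entered the further analyses. The Procedure section gives the reduced counts as the participants "for the experimental group (28 female, 3 male), and 34 participants for the control group (29 female, 5 male) were included for the study", without mentioning the 81.

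The Data Analysis section names the checking tools: "Before conducting parametric tests, the Shapiro-Wilk test, box plots, and skewness and kurtosis scores were used to check for normal distribution". For the performance tasks it says that "the skewness and kurtosis of the data fell within an acceptable range for applying parametric tests", citing a textbook and giving no numerical limit. None of these tools is tied to a criterion for removing a person. The section does not say whether normality was assessed before or after the removals. The efficacy analysis is then described: "2 x 2 mixed design repeated measure ANOVAs were conducted to examine the group" and time effects, with autistic-trait covariates. No second analysis set or sensitivity analysis appears. The participant flow figure is not shown in the copy reviewed and may list the exclusions.

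**The concern.** These people were randomised, stayed to the end and supplied posttest data. They were removed after the data were seen, and the loss fell mainly on the control arm. Outcome values are the natural reading of what triggered removal, although the text does not say so and autistic-trait scores were also measured. If removal depends on the outcome and differs by arm, the groups compared are no longer those that randomisation produced. The group-by-time contrast can then be shifted, its standard error can be too small, or both.

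Two further consequences follow. If normality was checked after removal, it is partly a product of the removal and cannot justify it. The exclusions also turn a visibly unequal 33 against 48 into a near-balanced 31 against 34, which hides the difference in completion between the arms.

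**Working it through.** **Counts (Participants section).** The sex breakdown agrees with the analysed totals: 28 + 3 = 31 and 29 + 5 = 34.

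| | Experimental | Control | Total |
|---|---|---|---|
| Randomised | 89 | 89 | 178 |
| Completed posttest | 33 (37.1%) | 48 (53.9%) | 81 |
| Analysed | 31 | 34 | 65 |
| Dropped after completion | 33 − 31 = 2 | 48 − 34 = 14 | 16 |
| Dropped, share of completers | 2/33 = 6.1% | 14/48 = 29.2% | 16/81 = 19.8% |

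- Fisher exact test on 2/33 against 14/48: p = .011. The control rate is 29.2/6.1 = 4.8 times the experimental rate.
- Removals expected if unrelated to arm: 16 × 33/81 = 6.5 and 16 × 48/81 = 9.5, against 2 and 14 observed.
- The 14 are 14/89 = 15.7% of the randomised controls.
- Completion by arm, 33/89 against 48/89: Fisher p = .035. Posttests missing: 178 − 81 = 97 (54.5%).
- Analysed share of those randomised: 31/89 = 34.8% and 34/89 = 38.2%, so the arms look alike after exclusion.

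**Simple bound on a shift.** Suppose the dropped people lie 1 SD from those kept, in the same direction in both arms. Dropping them moves the control mean by 14/48 = 0.29 SD and the experimental mean by 2/33 = 0.06 SD, a net 0.23 SD. The 1 SD is an assumption, and the result scales with it.

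**Null simulation.** There is no true effect, and 33 and 48 people have normal pretest and posttest scores. The 2 and 14 most extreme are removed. Change is then compared by t-test, which is equivalent to the 2 x 2 group-by-time F test. The pretest-posttest correlation is set at (.68 + .66 + .61)/3 = .65, the mean of the DASS-21 test-retest values in the Materials section ("for depression, .66 for anxiety, and .61 for stress" ends that list). Using it here is an assumption. Each one-outcome scenario had 40,000 runs. SD means that of a single score.

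| One outcome triggers removal | Type I error (nominal 5%) | Shift in contrast |
|---|---|---|
| Two-sided, pooled or fixed mean | about 5% (4.7–5.9% over repeat runs) | none |
| Two-sided, own-arm mean, pretest or posttest | 6.3% | none |
| Two-sided, own-arm mean, either time | 8.4% | none |
| Two-sided, own-arm mean, change | 16.8% | none |
| Two-sided, own-arm median, change | about 21% (20.5–21.8% over repeat runs) | none |
| One tail, pretest or posttest | 9.5–9.9% | 0.12 SD |
| One tail, either time | 5.0–7.7% | none |
| One tail, change | about 43% | 0.30 SD |

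The second set lets any of nine outcomes trigger removal: DASS-21 total, its three subscales, WCST, N Back, Go/No Go, Eyes Test and SAM. Cross-correlation is assumed to be .3, with 12,000 runs per scenario. Two-sided removal gives 4.9–8.6%. One-tail removal gives 5.2–6.4% with at most a 0.07 SD shift (posttest or either time), or 13–14% with a 0.15 SD shift (change).

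**Check of the remedy.** With all 81 kept and skewed null data (lognormal, sigma .6; 4,000 runs), type I error is 4.7% with HC3 standard errors and 5.2% with a permutation test. Non-normality therefore does not require removing anyone.

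**The case against.** The strongest reply is about size. The largest figures (16.8%, about 21%, about 43%, and 13–14% for nine outcomes) all need removal to be triggered by change scores, which the plan never mentions. Its checks concern questionnaire and task scores. Under score-based triggers the inflation is none to modest, at most 9.9%. Removing 14 of 48 on a single normal variable is also unrealistic: a conventional 1.5-IQR box-plot rule (an assumption) would flag about 0.6 of 48. Over 18 normal variables (nine outcomes, two times, correlation .3) it would flag about 9 of 48 and 8 of 33, so removal over several outcomes is more plausible, and there the inflation is smaller. The nine-outcome model is rough: a scale total sits beside its own subscales, SAM counts once although valence is scored by emotion, and autistic traits and covariates are left out. The flow figure may itemise the exclusions. Finally, the 97 missing posttests are a larger loss than these 16.

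Much of this stands as a limit on magnitude. The simulations are illustrations, and the high figures should be read as conditional on a change-score trigger. The objection does not remove the concern. The same box-plot reckoning gives about 8 removals in the experimental arm, where 2 occurred, so it does not explain the imbalance. An itemised figure would disclose the reasons but would not supply an analysis of all 81. Missing posttests cannot be recovered, whereas these 16 people have data and can be restored. Power is not the issue: both 65 and 81 exceed the 44 that the plan calls for.

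**Conclusion.** The concern holds. The counts follow directly from the Participants section, and no visible text gives a removal rule or an analysis of all 81 completers. Exclusion took 29.2% of control and 6.1% of experimental completers (p = .011), which shows imbalance and says nothing about intent. The direction and size of any bias cannot be known from the documents. They range from nil, if the trigger is unrelated to change, to severe, if one tail of change was trimmed (about 43% false positives and a 0.30 SD shift in the illustration). Those figures assume normal data and a pretest-posttest correlation of .65. Because the only efficacy analysis described uses this reduced set, the result cannot be relied on until it is shown in all completers. This must be fixed.

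**What to change.** - Remove the outlier and normality exclusion from the main analysis. Keep at least all 81 completers, and delete values only where a data error can be verified.
- Handle non-normality through inference: HC3 standard errors, bootstrap or permutation. Any of these will serve.
- Report the 65-person set only as a sensitivity analysis. List each exclusion by arm, variable, time point, cut-off and reason, and state whether the decision was made blind to arm.
- State whether the reported normality results were obtained before or after the removals.
- Say plainly that 81 is a minimum. Completion differs by arm, and keeping all completers does not cure that separate selection. All participants completed the pretest before assignment (Procedure section), so add an analysis of all 178 randomised, such as a likelihood-based mixed model or multiple imputation, with its missing-data assumption stated.

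The cost is re-running models on data already held. Residual variance will be somewhat larger because extreme values are retained, and selection from the 97 missing posttests remains in any completer analysis.

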The Wisconsin Card Sorting Task (WCST) is a cognitive flexibility performance task that was first developed by Berg in 1948. During the task, 200 cards in two blocks are displayed on the screen and the sorting rule changes after every 10 cards. Participants are expected to learn from feedback and adapt the rules during the task by trial and error. They need to match the cards according to their color, number, and shape. The task measures the error rates of the participants. Participants receive feedback only on the accuracy of their sorting, which helps them understand and adjust the current sorting rule. Feedback is given after each card selection.

N Back Task (Kirchner, 1958)

Working memory was evaluated through the N Back Task (Kirchner, 1958) in three different conditions - one back, two back, and three back. In this study, the $n = 2$ rule was applied. A sequence of stimuli was displayed one by one, and participants had to decide if the presented stimuli were the same as the stimuli that appeared in N trials earlier. The complete stimulus sequence consists of 15 letters and each stimulus was displayed for 500 milliseconds. Participants had three seconds to react (3000 milliseconds) and a new letter appeared every three seconds (3000 milliseconds). The letters A, B, C, D, E, H, I, K, L, M, O, P, R, S, and T were used in the sequence. There were eight blocks, with each block containing 50 trials. False errors were measured.

Go / No Go Task (Donders, 1969)

Go / No Go Task was used to measure inhibition. The task requires participants to respond as quickly and accurately as to the presented target stimulus (“go” trials) but avoid responding to non-target stimulus (“no go” trials). Participants need to respond in 2000 milliseconds when the “go” sign is presented and avoid responding when “no-go” is presented. There are 12 blocks of 50 trials each. Commission errors (i.e., incorrectly responding to no-go trials) were measured.

The Eyes Test - for Adults (Baron-Cohen et al. 2001b; Girli, 2014)

The Eyes Test is a performance task for emotion recognition which is widely regarded as an indicator of cognitive empathy. In this test, participants were presented with a series of 36 black-

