were used in the analyses for each EF task based on previous intervention studies (Chooi & Logie, 2020; de Vries et al., 2015; Macoun et al., 2021; Maraver et al., 2016). While accuracy was used for cognitive empathy and summing scores of images in affective empathy entered as dependent variables.

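### Go/No-Go inhibition is scored on commission errors alone, so responding less often counts as better inhibition and the plan has no check for it

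*Combined protocol and SAP*

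**What the plan says.** The section on the Go / No Go Task sets two demands. On go trials, "The task requires participants to respond as quickly and accurately as to the presented target stimulus", within 2000 ms; on no-go trials, the participant withholds. On length it says: "There are 12 blocks of 50 trials each". The split between go and no-go trials is not given. The only outcome named is: "Commission errors (i.e., incorrectly responding to no-go trials) were measured".

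For the N Back Task, "participants had to decide if the presented stimuli were the same as the stimuli that appeared in N trials earlier". The length is given as: "There were eight blocks, with each block containing 50 trials". The only outcome named is: "False errors were measured". The term is not defined, and the section does not say whether participants answered every trial or only pressed for a match.

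The introduction to Performance Tasks says "we recorded the errors for each task based on previous intervention studies", and Data Analysis says that errors "were used in the analyses for each EF task based on previous intervention studies". These scores are the dependent variables in the 2 x 2 (group by time) mixed ANOVAs for inhibitory control and working memory under hypothesis 2. Neither task description nor Data Analysis mentions omission errors, hit rate, reaction time, a sensitivity index such as d', or a minimum go-response rate.

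**The concern.** A Go/No-Go task has two halves, and the score uses only one of them. Fewer responses on no-go trials can mean better inhibition. They can also mean that the participant has become more cautious, slower or less engaged and responds less to everything. The second explanation leaves a trace in missed go trials and go reaction time, but the plan looks at neither.

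This affects the group comparison only if the change in response style differs between arms. That is plausible here. Under Procedure, one arm trained for six weeks with weekly progress checks, reminder messages and phone calls, while the other waited, and a waiting list cannot conceal allocation from participants. Training might make responding more careful; waiting might reduce engagement at posttest. The first would favour training and the second would work against it. What is at stake is the inhibition part of hypothesis 2. The DASS-21 outcomes of the primary aim are not touched.

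**Working it through.** The plan states no figure for this point that could be reproduced, so the check illustrates how far a commission score can move when ability does not.

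**Inputs from the documents.** Go/No-Go: 12 x 50 = 600 trials. N-back: 8 x 50 = 400 trials.

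**Assumptions (not in the documents).** Equal-variance signal-detection model; d' fixed at 2, 2.5 or 3; response criterion c moving from 0 to 0.3 or 0.5 (less willing to respond); 70% go trials where counts are shown.

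**Formulas.** Commission rate = Φ(−d'/2 − c). Go hit rate = Φ(d'/2 − c). Sensitivity d' is the same before and after by construction.

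| d' | c | commission rate | drop from c = 0 | go hit rate |
|---|---|---|---|---|
| 2.0 | 0 | 15.9% | – | 84.1% |
| 2.0 | 0.3 | 9.7% | 39% | 75.8% |
| 2.0 | 0.5 | 6.7% | 58% | 69.1% |
| 2.5 | 0 | 10.6% | – | 89.4% |
| 2.5 | 0.3 | 6.1% | 43% | 82.9% |
| 2.5 | 0.5 | 4.0% | 62% | 77.3% |
| 3.0 | 0 | 6.7% | – | 93.3% |
| 3.0 | 0.3 | 3.6% | 46% | 88.5% |
| 3.0 | 0.5 | 2.3% | 66% | 84.1% |

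The percentage drop does not depend on the go share, because it compares two rates on the same no-go trials.

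**In counts.** At d' = 2.5 with 70% go trials (180 no-go, 420 go), moving c from 0 to 0.3 takes commissions from 19.0 to 10.9 and omissions from 44.4 to 71.8. Total errors rise from 63.4 to 82.7, so the analysed score improves while overall accuracy worsens. That rise in the total depends on the starting point. From c = −0.6 to −0.3, commissions fall from 46.4 to 30.8 (34%), omissions rise from 13.5 to 25.4, and the total falls slightly, from 59.9 to 56.2. In every case commissions fall, omissions rise and d' is unchanged.

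**Limiting case.** A participant who never responds makes 0 commission errors, the best possible score.

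**N-back.** The result depends on what the undefined term means. Take d' = 2, an assumed 30% targets (120 targets, 280 non-targets) and c from 0 to 0.5:
- If only false alarms are counted: 44.4 to 18.7, a 58% drop, while misses rise from 19.0 to 37.0.
- If all errors are counted: 44.4 + 19.0 = 63.5 (before rounding) to 18.7 + 37.0 = 55.7, a 12% drop.

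Under the second reading misses are already in the score and most of the distortion goes.

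**The case against.** Commission errors are a recognised index of inhibition, and the plan gives a reason for error scoring: standardised measurement in line with earlier intervention studies. The instruction to be fast as well as accurate, with a response deadline, discourages withholding. A shift in response style common to both arms cancels in the group-by-time test, and nothing shows a differential one. The size of the shift above is assumed. These are secondary outcomes.

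All of this stands, and it limits the point to using commissions alone, without a companion measure. Precedent supports comparability, but it does not show that a fall in commissions reflects inhibition. The instruction asks for go responses, but the outcome does not check that they were given.

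Four stronger readings are tempting and are not supported:
- A reader might infer that N-back has the same fault. The text does not establish this: the error term is undefined, and the same-or-not decision could have been answered on every trial.
- A reader might infer that the trial's inhibition result is a response-style artefact. The documents show no such shift.
- A reader might infer that the remedy is only re-scoring of data in hand. The documents say that errors were recorded; they do not say that go hits, omissions or reaction times were stored.
- A reader might infer that d' should replace commission errors. Slowing within the 2000 ms window can raise hits and lower false alarms together, so d' would rise too. Only reaction time would show it.

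**Conclusion.** The point holds for Go/No-Go. The outcome is explicitly commission errors only, and no other measure in the plan would reveal a change in willingness to respond. The inhibition result can therefore be produced, or masked, by a differential change in response style, and the planned test could not show which. Under the stated model, with d' fixed at 2 to 3 and a shift of 0.3 to 0.5 from a neutral criterion, commission errors fall by 39% to 66% while go hits fall by about 5 to 15 percentage points. These are illustrations of sensitivity, not estimates of bias in this trial. For N-back, only a missing definition is established. This is a cheap improvement to a secondary conclusion.

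**What to change.** In Data Analysis:

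1. Keep commission errors as the Go/No-Go index, for comparability with the cited studies.
2. Run the same 2 x 2 group-by-time test on go-trial omission errors, and report go reaction time by group and time beside it. Give estimates with confidence intervals, since with 31 and 34 participants analysed a non-significant omission result would not by itself show that omissions were unchanged.
3. Claim improved inhibition only if fewer commissions are not accompanied by more omissions or slower go responses. d' may be added as a supporting analysis.
4. State whether go-trial responses were stored. If they were not, limit the conclusion to fewer commission errors.
5. For N-back, state whether the error score means false alarms or all errors, and give the response format. If it means false alarms, apply the same check with missed targets.

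Cost: a little more analysis and a few lines of text, provided the responses were stored, and a somewhat stricter condition for claiming an inhibition benefit.
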